# DOSE-PROPORTIONALITY AND INTRA-INDIVIDUAL VARIABILITY OF INTRACELLULAR TENOFOVIR DIPHOSPHATE AND EMTRICITABINE TRIPHOSPHATE IN HEALTHY VOLUNTEERS

## LIST OF ABBREVIATIONS AND ACRONYMS

AE	adverse event
AIDS	Acquired Immunodeficiency Syndrome
aPTT	activated partial thromboplastin time
ALT	alanine aminotransferase
AST	aspartate aminotransferase
BV	bacterial vaginosis
Ca	calcium
CBC	complete blood count
CDC	Centers for Disease Control and Prevention
CORE	(HPTN) Coordinating and Operations Center
Cl	chloride
CRPMC	(NIAID) Clinical Research Products Management Center
CT	Chlamydia (Chlamydia trachomatis)
DAIDS	Division of AIDS
DOT	Directly observed therapy
EAE	expedited adverse event (reporting)
EC	ethics committee
FDA	(United States) Food and Drug Administration
FTC	emtricitabine
FTC-TP	emtricitabine triphosphate
GC	gonorrhea ( Neisseria Gonorrhoeae )
GCLP	good clinical laboratory practice
GCP	good clinical practice
HBsAg	hepatitis B surface antigen
HC03	bicarbonate
HIV	Human Immunodeficiency Virus
HPTN	HIV Prevention Trials Network
IDS	investigational drug service
IRB	institutional review board
K	potassium
LDMS	Laboratory Data Management System
LL	local laboratory
LLN	lower limit of normal
Na	sodium
NAAT	nucleic acid amplification test
NIAID	(United States) National Institute of Allergy and Infectious Diseases
NIH	(United States) National Institutes of Health

NL	(HPTN) Network Laboratory
NSAID	Non-steroidal anti-inflammatory drug
OHRP	Office for Human Research Protections
PD	pharmacodynamics
PK	pharmacokinetics
PoR	pharmacist of record
PrEP	pre-exposure prophylaxis
PSRT	Protocol Safety Review Team
PT	prothrombin test
QA	quality assurance
QC	quality control
RPR	rapid plasma reagin test for syphilis
RTI	reproductive tract infection
RSC	Regulatory Support Center (formerly RCC)
RUQ	right upper quadrant
SAE	serious adverse event
SDMC	(HPTN) Statistical and Data Management Center
SMC	Study Monitoring Committee
SOP	standard operating procedures
SSP	study specific procedures (manual)
STI	sexually transmitted infection
TDF	tenofovir disoproxil fumarate
TDF/FTC	Truvada® (tenofovir disoproxil fumarate and emtricitabine in fixed dose combination)
TFV	tenofovir
TFV-DP	tenofovir diphosphate
Trich	trichomoniasis ( Trichomonas vaginalis )
ULN	upper limit of normal
UTI	urinary tract infection

## HPTN 066

### DOSE-PROPORTIONALITY AND INTRA-INDIVIDUAL VARIABILITY OF INTRACELLULAR TENOFOVIR DIPHOSPHATE AND EMTRICITABINE TRIPHOSPHATE IN HEALTHY VOLUNTEERS

#### TERMINOLOGY FOR TENOFOVIR, EMTRICITABINE, AND THEIR DERIVATIVES

Abbreviation	Compound name	Comments
TDF	Tenofovir disoproxil fumarate	This is the inactive, oral formulation of tenofovir (trade name: Viread®). The ester form enhances oral absorption and bioavailability. TDF is rapidly metabolized after dosing to the de-esterified pro-drug, tenofovir (TFV), which is also inactive.
TFV	Tenofovir	This is the inactive, de-esterified form of TDF. This form of the drug that is measured in serum, blood, other body fluids, and tissue samples.
TFV-DP	Tenofovir diphosphate	This is the active, phosphorylated form of tenofovir that is generated in cells. This is the form of the drug that is measured in cells (e.g., PBMCs). It is rapidly dephosphorylated to the inactive form outside of cells, and has a very short half-life outside of cells in tissue.
FTC	Emtricitabine	This antiretroviral drug (trade name: Emtriva®) is co-formulated with TDF in Truvada® (TDF/FTC). FTC is an inactive pro-drug that is activated in cells by phosphorylation. This is the form of emtricitabine that is measured in serum, blood, other body fluids, and tissue samples.
FTC-TP	Emtricitabine triphosphate	This is the active form of FTC that is generated in cells. This is the form measured in cells (e.g., PBMCs).
Truvada®	Tenofovir plus emtricitabine	This is the co-formulated drug produced by Gilead Sciences, Inc. Each pill contains 300 mg of TDF and 200 mg of FTC.

## HPTN 066

## SCHEMA

**Purpose:** Describe the dose-proportionality and intra-individual variability of tenofovir diphosphate (TFV-DP) and emtricitabine triphosphate (FTC-TP) at steady-state in healthy human participants taking Truvada® (FTC 200mg/TDF 300 mg) under direct observation.

**Design:** Phase 1, multi-site, open label, randomized, 4-arm, dose-ranging, pharmacokinetic (PK) study.

**Study Population:** HIV-uninfected, healthy, sexually-active volunteers, including both men and women recruited from two sites in the United States (U.S.).

**Study Size:** 32 participants distributed into four 8-person cohorts with 4 men and 4 women per cohort. 16 of the original 32 participants (2 men, 2 women per dosing cohort), will undergo intensive tissue sampling.

**Treatment Regimen:** Research participants will receive doses under the direct observation of study personnel for 5 weeks. Research participants will be enrolled randomly into one of four study arms:

1. FTC 200 mg/TDF 300 mg, one tablet orally once weekly for 5 weeks
2. FTC 200 mg/TDF 300 mg, one tablet orally twice weekly for 5 weeks
3. FTC 200 mg/TDF 300 mg, two tablets orally twice weekly for 5 weeks
4. FTC 200 mg/TDF 300 mg, one tablet once daily for 5 weeks

**Study Duration:** Approximately 12 months total. Accrual will require approximately 6 months. Each participant will be followed for approximately 2 months (screening, treatment, and follow-up).

**Primary Objectives:**

1. Assess dose-proportionality of intracellular TFV-DP and FTC-TP from weekly to daily dosing.
2. Describe intra-individual variability in intracellular TFV-DP and FTC-TP concentrations at steady-state (comparison of Day 28 and Day 35)

**Secondary Objectives:**

1. Describe the relationship between pre-dose ( $C_\tau$ ) and decaying concentrations of TFV, FTC, and their phosphorylated derivatives (TFV-DP and FTC-TP) in blood serum, peripheral blood mononuclear cells (PBMCs), CD4+ blood cells, total tissue cells, CD4+ tissue cells, tissue homogenate, semen, and luminal fluid at steady-state (Day 35 [pre-dose] and Day 49 [decaying, greater than one half-life for TFV-DP]).
2. Describe differences in intracellular TFV-DP and FTC-TP steady-state  $C_\tau$  between men and women.
3. Characterize the safety profiles of four different TDF/FTC regimens for pre-exposure chemoprophylaxis (PrEP).

**OVERVIEW OF PARTICIPANT DISTRIBUTION AND STUDY DESIGN**

**A) Distribution Scheme**

## OVERVIEW OF PARTICIPANT DISTRIBUTION AND STUDY DESIGN (cont.)

### B) Study Design

## **1.0 INTRODUCTION**

### **1.1 Background and Prior Research**

#### **1.1.1 Using PrEP for HIV Prevention**

With 2.5 million new HIV infections expected in the coming year, there is an urgent need to find effective ways to reduce HIV transmission (UNAIDS, 2008). Pre-exposure antiretroviral chemoprophylaxis (PrEP) has been shown to decrease viral transmission in animal models (Garcia-Lerma et al., 2008; Subbarao et al., 2007; Veazey et al., 2005), and post-exposure prophylaxis has decreased HIV transmission in health care workers (Cardo et al., 1997) and men who have sex with men (MSM) (Schechter et al., 2004). The first human efficacy trials of daily PrEP are likely to be completed by late 2010. These trials are only evaluating daily dosing. For the majority of the “at-risk” populations, HIV risk-taking is unlikely to occur on a daily basis. Therefore, less frequent drug dosing (i.e., intermittent PrEP) will result in decreased drug costs and lower risk of toxicity. However, any benefit from intermittent PrEP as compared to daily PrEP could be mitigated by an increased risk of HIV infection if intermittent PrEP were to provide insufficient drug concentrations in relevant tissues. The most encouraging data suggesting that intermittent PrEP may be a plausible prevention strategy comes from a study by Garcia-Lerma and colleagues (Garcia-Lerma et al., 2009), in which monkeys were well-protected from SIV infection after receiving one dose of tenofovir disoproxil fumarate (TDF) plus emtricitabine (FTC) at either 7 days, 3 days, or 2 hours pre-SIV exposure followed by a second dose 2 hours post-exposure. While encouraging, these data cannot be directly extrapolated to humans due to the differences in simian anatomy and pharmacokinetics as well as differences between HIV and the SIV challenge strain. Moreover, an efficacy trial of intermittent PrEP can be initiated only after the following pharmacological issues are understood. First, the overall drug concentrations achieved in humans receiving various intermittent PrEP regimens must be understood. Secondly, the intra-individual variability exhibited between proposed intermittent PrEP regimens must be carefully considered. Lastly, drug concentrations must then be evaluated in light of *in vitro* and animal model data to estimate the range of concentrations that may be necessary to provide preventive concentrations of the relevant antiretroviral drugs.

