## **1.2 Rationale**

### **1.2.1 Overall Study Rationale**

This PK study is designed to establish the dose-proportionality of TFV and FTC (serum and intracellular forms) with daily to weekly dosing. This information is essential to (1) employ drug concentration as an adherence measure in future PrEP studies, and (2) to estimate the anticipated concentration of parent and active moieties of TFV and FTC in intermittent PrEP regimens associated with full adherence to a prescribed regimen. In addition, intra-individual variability will be assessed to improve sample size estimates in future PrEP studies that use drug concentration as an adherence measure or where PK-PD correlations are planned. The dose-proportionality of intra-cellular phosphates of the two components of the study product has not previously been established. Given the complexity of movement of these drugs between body compartments (central compartment, vaginal mucosal tissue, vaginal lumen, gastrointestinal mucosal tissue, gastrointestinal lumen), into cells within these compartments, and intra-cellular phosphorylation, it is possible that non-dose proportional kinetics, such as mixed or zero-order saturable processes may be operating.

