### 1.2.3 Dosing Duration Rationale

Dose-proportionality can be assessed at any point of observation following initiation of dosing. Intra-individual variability, however, can best be assessed at two sampling times not anticipated to vary based on PK principles. Essentially, by definition, this condition is achieved when steady-state has been reached. This study requires direct observation of dosing to rule out adherence as a cause for variation in drug concentrations. Therefore, we plan to begin sampling for intra-individual variability assessments as early as possible after dosing, balancing logistical difficulties (up to daily dosing for study staff and research participants) and PK limitations. Intracellular TFV-DP concentrations are estimated to achieve between 93% and 97% of steady-state Cmin (trough) concentrations after 4 half-lives and 5 half-lives, respectively, have elapsed after initiation of Truvada® dosing. Based on an estimated 150-hour TFV-DP intracellular half-life (FTC-TP will achieve steady-state earlier, given its far shorter 36-hour half-life), the 4 and 5 half-life points coincide with 28 and 35 days of dosing. Laboratory assay variation for all of the assays planned for this study are more than twice as large as the very small 4% difference in concentrations that we expect to measure between Day 28 and Day 35. Accordingly, we plan to dose for 35 days, and to use samples from Day 28 and Day 35 for our intra-individual variability estimates. One could argue for longer periods of dosing to further reduce differences between doses in the asymptomatic approach to a true steady-state, but we believe that our proposed plan provides a reasonable balance between logistical complexity (daily dosing under direct observation) and reasonable experimental variation.

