## **2.0 STUDY OBJECTIVES AND DESIGN**

### **2.1 Primary Objectives**

The primary objectives of this study are to:

- Assess dose-proportionality of intracellular TFV-DP and FTC-TP from weekly to daily dosing (Arms 1-4).
- Describe intra-individual variability in intracellular TFV-DP and FTC-TP concentrations at steady-state (comparison of Day 28 and Day 35).

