**Table 7-3. Biological matrices for analyses**

	Blood Samples			Vaginal, Rectosigmoid, and Semen Samples			
	Serum	PBMC	CD4+ blood cells	Total tissue cells	CD4+ tissue cells	Luminal fluid & semen	Homogenate
TFV-DP		X	X	X	X		X
FTC-TP		X	X	X	X		X
TFV	X					X	X
FTC	X					X	X

Descriptive statistics, such as means, medians, variance, and interquartile ranges, will be used to summarize Day 35 pre-dose concentration ( $C_t$ ) by gender and by dose arm. Simple comparison of median concentration level between dose arms will be done with standard non-parametric methods. Gender- or dosing-specific CVs of Day 35 pre-dose concentration ( $C_t$ ) will be estimated. These CV estimates would be informative to the future studies even if dose proportionality does not hold.

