### 7.6.1.2 Intra-Participant Variability

Intra-participant variability will be described by the coefficient of variation of concentrations assessed on Day 28 and Day 35, which are assumed to be at steady-state, using data from all evaluable participants across dosing arms. We will confirm that steady-state was achieved by evaluating drug concentration data from Day 7, 14, and 21. If the dose-proportionality is established as described earlier, then dose-adjusted concentrations will be used for a more robust assessment. These variability estimates will be calculated for all analytes in blood and blood cells. As supportive evidence, the accumulation data from Day 7, 14, and 21 will also be used to estimate the elimination rate constant. Tissue and luminal assessments cannot be calculated due to the absence of multiple steady-state samples.

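### The within-person CV is planned only as a figure pooled over dosing arms, although weekly troughs are likely to vary relatively more than daily ones and the estimate is meant for planning later studies

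*Protocol*

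**What the plan says.** Protocol section 1.1.1 lists pharmacological questions to settle before an efficacy trial of intermittent PrEP. The second is that "the intra-individual variability exhibited between proposed intermittent PrEP regimens must be carefully considered". Section 1.2.1 gives the practical use: "intra-individual variability will be assessed to improve sample size estimates in future PrEP studies that use drug concentration as an adherence measure". Section 1.1.6 makes the same link to sample size.

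The second primary objective (section 2.1) begins: "Describe intra-individual variability in intracellular TFV-DP and FTC-TP concentrations at steady-state (comparison of Day 28 and Day 35". It does not mention regimen.

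Section 7.6.1.2 carries out that objective. It describes the CV of the Day 28 and Day 35 concentrations "using data from all evaluable participants across dosing arms". Its only refinement is: "If the dose-proportionality is established as described earlier, then dose-adjusted concentrations will be used for a more robust assessment". It plans no within-person CV by arm or by dosing frequency.

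Reporting by arm is specified elsewhere. Section 7.6.1.1, below Table 7-3, plans "Gender- or dosing-specific CVs of Day 35 pre-dose concentration". Those CVs use one day per person, so they measure spread between people. Section 7.6.2.1 summarises half-life both per arm and overall.

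**The concern.** A pooled within-person CV is a good planning value only if relative variability is similar in all arms. The protocol's own kinetics give reason to doubt that.

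A trough sums what remains of all earlier doses. With daily dosing many doses contribute, and chance variation between them partly averages out. With weekly dosing the last dose dominates, and the sample is taken 168 hours after it, so a small change in elimination rate moves the trough more.

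Dose adjustment cannot remove this. Multiplying both of a participant's values by a constant leaves that participant's CV unchanged, and the difference between regimens lies in the relative variability itself.

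A later adherence or PK-PD study will probably use one regimen. If it takes its within-person CV from the pooled figure, it may plan with too large a value for daily dosing or too small a value for weekly dosing. A pooled figure also cannot show whether the regimens differ.

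**Working it through.** **Inputs from the protocol.** Half-lives (section 1.2.3 and Table 1-1): "Based on an estimated 150-hour TFV-DP intracellular half-life" and, for FTC-TP, "given its far shorter 36-hour half-life". Dosing intervals τ of 168 h (weekly) and 24 h (daily) come from Table 1-1. Section 1.2.3 puts assay variation at more than twice a 4% difference, so above about 8%. Arm size is 8.

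**Inputs assumed.** The protocol states no within-person CV for dose uptake or elimination. I take a source CV c of 10% to 40% and an assay CV of 8% to 15%. Twice-weekly doses are placed on Days 0 and 3 of each week.

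**Step 1: the protocol's own figure.** R_ac = 1/(1 − e^(−kτ)), with k = ln 2/half-life.
- FTC-TP: 2.70 daily, 1.04 weekly.
- TFV-DP: 9.53 daily, 1.85 weekly.

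These agree with Table 1-1 after rounding.

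**Step 2: share of the steady-state trough from the last dose**, 1 − e^(−kτ) = 1/R_ac.
- FTC-TP: 0.961 weekly, 0.370 daily.
- TFV-DP: 0.540 weekly, 0.105 daily.

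**Step 3: Day 35 trough CV per unit of source CV, no assay error.** Let w = e^(−k × time since dose), summed over the scheduled doses.
- Model A, independent dose-to-dose variation: c × √(Σw²)/Σw.
- Model B, within-person variation in k: c times the sensitivity of log trough to log k. At steady state this sensitivity is kτ/(1 − e^(−kτ)).

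| | Weekly | Twice weekly | Daily | Weekly:daily |
|---|---|---|---|---|
| FTC-TP, A | 0.961 | 0.793 | 0.476 | 2.02 |
| FTC-TP, B | 3.367 | 2.258 | 1.249 | 2.70 |
| TFV-DP, A | 0.621 | 0.445 | 0.240 | 2.58 |
| TFV-DP, B | 1.356 | 1.162 | 0.975 | 1.39 |

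**Step 4: add assay CV of 8% to 15% in quadrature.** The weekly:daily ratios become:
- FTC-TP: 1.13 to 1.90 (A), 1.89 to 2.67 (B).
- TFV-DP: 1.07 to 2.09 (A), 1.13 to 1.38 (B).

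**Step 5: allow for doses shared by the two troughs.** Under model A, steady-state troughs one week apart correlate at e^(−168k): 0.039 for FTC-TP and 0.460 for TFV-DP. The within-person SD seen in a Day 28/Day 35 pair therefore shrinks in every arm, and assay error weighs more. Recomputed from the scheduled doses, the model A ratios are 1.13 to 1.90 for FTC-TP (unchanged) and 1.04 to 1.88 for TFV-DP.

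**Step 6: where the pooled value falls.** FTC-TP, model A, using the step 3 factors:
- c = 20%, assay 8%. Weekly √((0.20 × 0.961)² + 0.08²) = 20.8%; twice weekly 17.8%; daily 12.4%. Root mean square over four equal arms: √((20.8² + 2 × 17.8² + 12.4²)/4) = 17.5%. That is 1.4 times daily and 0.84 times weekly.
- c = 10%, assay 15%. Weekly 17.8%, daily 15.7%, pooled 16.9%. That is 1.08 times daily and 0.95 times weekly.

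**Step 7: precision.** Each participant's pair gives one degree of freedom. The 95% limits for an SD are the estimate times √(df/χ²): 0.68 to 1.92 on 8 df, 0.74 to 1.52 on 16 df, 0.80 to 1.32 on 32 df.

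**The case against.** The strongest reply is that nothing is contradicted. Section 1.1.1 is background about a future trial, and the objective in section 2.1 asks only for a description, without regimen. A table by arm is not excluded and could be set out in the SAP. This stands in part: there is no breach of an objective. But section 7.6.1.2 is not merely silent. It specifies data across arms, while sections 7.6.1.1 and 7.6.2.1 ask for arm-level results where these are wanted.

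Second, section 1.1.1 speaks of intermittent regimens, so its contrast is weekly against twice weekly. For FTC-TP without assay error that ratio is 0.961/0.793 = 1.21 (A) or 3.367/2.258 = 1.49 (B), less than weekly against daily. This stands. Nor were the regimens chosen to compare variability: section 1.2.2 says they were selected to assess dose-proportionality.

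Third, the size depends on assumptions. Occasion-level noise common to all arms would shrink it further: adding an illustrative 20% to a 20% dose CV and a 10% assay CV gives an FTC-TP ratio of √(0.192² + 0.10² + 0.20²)/√(0.095² + 0.10² + 0.20²) = 1.21. This stands.

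Fourth, section 1.1.7 favours TFV-DP for adherence monitoring, where the effect is generally smaller, and weekly FTC-TP has an accumulation index of only 1.0. This limits the practical damage but does not remove the gap.

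A reader might infer that the half-lives alone prove a two-fold difference, that the pooled CV is wrong for both weekly and daily dosing, or that later studies would be mis-sized by a known multiple. The documents support none of these. Each needs within-person variance components that the protocol does not give, and a pooled value is an average lying between the arms.

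**Conclusion.** The point holds as a worthwhile improvement to the analysis of the second primary objective. Section 7.6.1.2 pools within-person variability across dosing arms and provides no estimate by regimen, although the estimate is meant for planning. The direction is well supported: weekly troughs were relatively more variable than daily ones in every case computed, and dose adjustment does not alter this.

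The size is uncertain. With 8% to 15% assay CV and a source CV of 10% to 40%, the FTC-TP weekly:daily ratio is about 1.1 to 2.7. For TFV-DP it is generally smaller, about 1.0 to 1.9 under model A after allowing for shared doses and 1.1 to 1.4 under model B. At the low end pooling costs little. These ranges rest on first-order decay with the Table 1-1 half-lives and on the assumed CVs, and they include no further noise common to all arms.

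**What to change.** In section 7.6.1.2, report the within-person CV of each blood analyte by dosing frequency: weekly (Arm 1, n = 8), twice weekly (Arms 2 and 3, n = 16) and daily (Arm 4, n = 8). Derive it from within-person variances of log concentration, with a confidence interval for each, and show the pooled value beside them, described as an average over regimens.

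Do not make use of the pooled value depend on a test of agreement. A two-sided 5% F test of weekly against daily variance, on 8 df each, has only about 44% power at a true SD ratio of 2.0 and 26% at 1.67, so apparent agreement would say little.

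The change needs wording only: no new data, visits or participants. The cost is precision, with 95% limits of about 0.68 to 1.92 times the estimate for the weekly and daily groups and 0.74 to 1.52 for twice weekly, against 0.80 to 1.32 for the pooled value.

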
#### **1.1.2 Significance of Determining Pharmacology of Intermittent PrEP**

The data generated by the proposed study will be used to develop a comprehensive multi-compartment pharmacokinetic (PK) model. Assuming dose proportionality is found, this model will be used to estimate extracellular and intracellular drug exposure in multiple compartments for any dose and dosing interval combination. This model will be critical to the following three areas: 1) developing an optimal pharmacology-based adherence intervention for future PrEP studies, 2) assessing adherence in ongoing studies with currently stored samples, 3) developing a

pharmacokinetic-pharmacodynamic (PK/PD) model to determine target intracellular drug exposures that prevent HIV infection.

### **1.1.3 Need for Accurate Adherence Data**

All large-scale PrEP trials will need to determine medication adherence accurately in order to interpret the success or failure of any pharmacologic intervention. Acquisition of HIV infection during such trials may result from failure to achieve protective drug concentrations at the site of action. This failure may be from either (1) full adherence that did not achieve adequate drug concentrations from the prescribed regimen, or (2) poor adherence to the prescribed regimen, resulting in concentrations too low to provide protection from HIV infection. Differentiating between these two etiologies of PrEP failure are impossible using traditional adherence measures [pill counts, medication history and computer chips in the cap of pill containers (e.g., MEMS caps)] as none of these actually document pill-taking behavior. Using a pharmacologic measure in combination with a robust PK model will allow interpretation of adherence using stored samples from completed studies, and will provide real-time information that could be used to guide behavioral interventions.

[figure not shown]
